## **7. Outcome Variables**

**Primary study variable**, amount of gas vaporized halogenated anaesthetic per minute anaesthesia.

### **Secondary study variables;**

1. Time needed to increase from Etaa 1 to Etaa 1.5 age adjusted MAC with a constant 1 L/min. and a dialled 3 MAC, the vaporiser set at 18 %, in conjunction to start of surgery
  - a. When the 1.5 Etaa has been achieved the gas setting should be adjusted in accordance to clinical needs throughout the surgery.
2. Time needed during wash-out, time from cessation of administration until reaching 0.2 MAC
  - a. Time from cessation of administration to awakening; extubation and able to state name and date of birth
  - a. Time to reach Aldrete > 8
  - b. Pain and need for analgesics and anti-emetics during the PACU stay
  - c. Follow-up of quality of recovery PQRS

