**Main measurements:**

Time to go from 1 to 1.5 MAC end-tidal concentration during controlled ventilation with a tidal volume of 6 ml/kg and a respiratory rate of 12 breaths per minutes.  
Amount anaesthesia agent consumed; Gram inhaled anaesthetic per minute anaesthesia.

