## **Objective**

To test the hypothesis that the Flow I breathing circle system without a below reservoir provides a faster and less anaesthetic vapour consuming wash-in and maintenance of  $E_{t_{\text{desflurane}}}$

The aim of the study is to compare gas kinetics, time needed in order to change the end-tidal concentration, and vapour consumption (and associated cost) between the novel Flow-I circle system and the standard anaesthesia equipment/machine at the centre (multi-centre study; 3 centres) during general anaesthesia for routine elective surgery in ASA 1-2 patients.

The study will compare The Flow I to a conventional anaesthetic machine including a breathing circle based on a below reservoir during routine desflurane with a fresh gas flow of 1 L/min in ASA 1-2 patients having elective surgery.

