#### **Inclusion criteria**

- Age 20 to 60 years
- BMI 20-30
- ASA 1-2

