## **8. Statistics**

As this is an explorative pilot study thus no formal sample size will be determined.

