### *Power calculation*

Based on the experience from pilot study a vaporizer consumption of 0.28 gr/min with a SD of 0.07 and the Flow-I being more efficient vapor injection providing an estimated 0.03 gr/min reduction of vapor a group size of 43 patients would be required in order to verify a significant difference  $p < 0.05$  at a power of 80%. A total of 2 x 43 in all 86 and a drop out / lost for follow-up of about 10-14 patients 100 patients will be recruited.

Comparison of normally distributed variables will be done by Student's t-test, of variables not following a normal distribution by Wilcoxon Test.

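### With a fixed 18 % dial, the 1 to 1.5 age-adjusted MAC wash-in time is expected to vary with age in both arms; the planned unadjusted test is valid but may give up a little precision that an age covariate would recover

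*Combined protocol and SAP*

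**What the plan says.** The points below are all from the combined protocol and SAP.

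- **Endpoint and setting.** Section 7, secondary variable 1, measures the time for end-tidal agent to rise from 1 to 1.5 "age adjusted MAC with a constant 1 L/min. and a dialled 3 MAC, the vaporiser set at 18" %. The thresholds are on an age-adjusted scale. The dial is described in two ways, as a MAC multiple and as a percentage, and the text does not say which governs.
- **Age range.** Section 3 admits "Age 20 to 60 years".
- **Analysis.** Section 8 states: "Comparison of normally distributed variables will be done by Student's t-test", and "of variables not following a normal distribution by Wilcoxon Test". It names no covariate.
- **Standing of the endpoint.** The primary variable in section 7 is "amount of gas vaporized halogenated anaesthetic per minute anaesthesia". Wash-in time is secondary there, but section 1 also lists it as a main measurement: "Time to go from 1 to 1.5 MAC end-tidal concentration during controlled ventilation".
- **Sample size.** Section 8 says "As this is an explorative pilot study thus no formal sample size will be determined" and then gives a calculation of 43 per group for vapour consumption. No SD, effect or power is given for wash-in time.

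**The concern.** A dial of 18 % equals three MAC only where 1 MAC is 6 %. If MAC falls with age, as an age-adjusted scale implies, a younger patient on 18 % has a larger absolute step to climb and fewer MAC multiples driving it. Wash-in is then slower in the young and faster in the old, whichever machine is used. A two-group test that ignores age treats this spread as noise.

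The stake is the width of the confidence interval for the outcome that most directly tests the faster wash-in part of the hypothesis. The sample size was chosen for another variable, so nothing in the plan secures precision for this one. Age must be known anyway to compute the endpoint, so the information is already in hand.

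**Working it through.** **The plan's own figure.** None exists for wash-in. The 43 per group in section 8 is for vapour consumption (difference 0.03 g/min, SD 0.07). The standard two-sided formula gives 2 × (0.07 × (1.96 + 0.84)/0.03)² ≈ 86 per group. The figure of 43 appears when the factor 2 is left out. That is a separate matter. Here 43 per arm is used only as the planned size.

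**Inputs from the documents.** Dial 18 %, thresholds 1 and 1.5 age-adjusted MAC, ages 20 to 60, 43 per arm.

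**Assumed inputs, not in the documents.**
- 1 MAC = 6 % at age 40 (18 %/3).
- MAC falls by a fraction s = 5, 6 or 7 % per decade.
- Single-compartment wash-in, with the same time constant τ at every age.
- Residual log-SD r = 0.3 or 0.5.
- Ages either uniform on 20 to 60, or clustered (normal, mean 45, SD 8.5, truncated to 20 to 60; actual SD 7.7 years).

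**Step 1: wash-in time by age.** With M = 6 × (1 − s)^((age − 40)/10), the time is t/τ = ln((18 − M)/(18 − 1.5M)). At age 40 this is ln(12/9) = 0.288.

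| s | t/τ at age 20 | t/τ at age 60 | ratio |
|---|---|---|---|
| 5 % | 0.346 | 0.242 | 1.43 |
| 6 % | 0.361 | 0.234 | 1.54 |
| 7 % | 0.376 | 0.226 | 1.66 |

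If the dial is three age-adjusted MAC, t/τ = ln((3M − M)/(3M − 1.5M)) = ln(2/1.5) = 0.288 at every age, and this age effect is zero.

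**Step 2: share of variance due to age.** The SD of ln t across ages, for s = 5/6/7 %, is 0.103/0.125/0.146 (uniform) and 0.068/0.082/0.096 (clustered). The share is SD²/(SD² + r²). For example, with uniform ages, s = 6 % and r = 0.3, it is 0.0156/(0.0156 + 0.0900), which is 14.7 % before rounding. In large samples the unadjusted standard error is larger by the factor 1/√(1 − share), here 1/√0.853 = 1.083.

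**Step 3: net of the parameter spent on age.** Simulation with 43 per arm (3,000 runs per setting), comparing log time unadjusted with log time adjusted for age:

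| Ages | r | share, s = 5/6/7 % | SE ratio, unadjusted/adjusted |
|---|---|---|---|
| Uniform | 0.3 | 10.6/14.7/19.2 % | 1.053/1.078/1.108 |
| Uniform | 0.5 | 4.1/5.8/7.9 % | 1.015/1.026/1.037 |
| Clustered | 0.3 | 4.9/6.9/9.3 % | 1.020/1.032/1.043 |
| Clustered | 0.5 | 1.8/2.6/3.5 % | 1.003/1.007/1.012 |

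Age adjustment on untransformed time gives a similar gain, about 1 to 7 % at s = 6 %, so the log scale is not what produces it.

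**Step 4: power, for illustration.** From a baseline set near 80 % (the plan states none), adjustment adds 1.5 to 6.6 points with uniform ages and 0.1 to 3.4 with clustered ages. The Monte Carlo error of each power is about 0.7 points. Type I error was 4.2 to 5.9 % for every method, so there is no sign that the planned tests are invalid.

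**The case against.** The strongest reply is that the documents fix neither the premise nor the size.

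- **The dial is ambiguous.** If three age-adjusted MAC is what is dialled, there is nothing to recover from this source. This stands, and the point is conditional for that reason. The percentage is the concrete instruction, so 18 % for all is the more natural reading.
- **The constant τ is an assumption.** The ratios 1.43 to 1.66 over four decades are about 9 to 14 % per decade (1.43^(1/4) = 1.09, 1.66^(1/4) = 1.14). If τ rose with age by that much, the effect would cancel. At half that rise, the log-SD at s = 6 % would halve and the uniform-age share would fall from 14.7 % to about 4 % (r = 0.3), or from 5.8 % to about 1.5 % (r = 0.5). A τ that falls with age would enlarge the effect. This stands too: the age trend is a model expectation, not something the plan states.
- **The range depends on what is varied.** With slopes of 3 to 9 % per decade and residual CV of 20 to 50 %, the large-sample reduction in standard error runs from under 1 % to 28 %. The top end needs the steepest slope and the smallest residual variation together.
- **Adjustment is optional.** The endpoint is secondary in a self-described exploratory pilot, and omitting a covariate from a randomised comparison is not an error. Agreed.

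These objections limit the size. They do not count against a one-parameter adjustment that leaves the comparison valid.

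A reader might also infer that the remedy needs centre terms, since the Objective refers to "the standard anaesthesia equipment/machine at the centre (multi-centre study; 3 centres"), or a ratio of geometric means. Neither is needed here. Two centre terms cost about 1 % of the standard error when centres do not differ, and can turn the smallest gains into a slight loss.

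**Conclusion.** The point holds as a low-cost improvement. If 18 % is dialled for every patient, wash-in time is expected to vary with age in both arms, and the unadjusted tests carry that variance as error. The unadjusted standard error is about 0 to 11 % larger over the main ranges examined (MAC slope 5 to 7 % per decade, residual log-SD 0.3 to 0.5, uniform or clustered ages, constant τ, 43 per arm). The gain is near zero when ages cluster and other variation is large, and zero from this source if the dial follows age-adjusted MAC.

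A reader might infer that the machine comparison is biased by age, or that the planned test is wrong. The documents do not support either: allocation is random, so age is balanced in expectation, and the planned tests are valid without adjustment. Nor do they support a claim that adjustment is certain to help by a given amount, because they give no wash-in SD, MAC-age slope or age distribution.

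**What to change.** In section 8, prespecify the wash-in comparison as a linear model of wash-in time on arm with age as a linear covariate, log-transforming time only if it is skewed. Report the arm difference with a 95 % CI, and keep the planned t-test or Wilcoxon test as a sensitivity analysis. In section 7, secondary variable 1, state whether the fixed 18 % or the age-adjusted multiple governs the dial.

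The cost is one model parameter and a sentence in each section. No data are added, since age is an entry criterion and is already needed for the endpoint. The downside is that the gain may be negligible.

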## **8. Statistics**

As this is an explorative pilot study thus no formal sample size will be determined.

### *Power calculation*

Based on the experience from pilot study a vaporizer consumption of 0.28 gr/min with a SD of 0.07 and the Flow-I being more efficient vapor injection providing an estimated 0.03 gr/min reduction of vapor a group size of 43 patients would be required in order to verify a significant difference  $p < 0.05$  at a power of 80%. A total of 2 x 43 in all 86 and a drop out / lost for follow-up of about 10-14 patients 100 patients will be recruited.

Comparison of normally distributed variables will be done by Student's t-test, of variables not following a normal distribution by Wilcoxon Test.

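### The planned 43 patients per group give about 50% power (two-sided), not the stated 80%, on the plan's own difference and SD

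*Combined protocol and SAP*

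**What the plan says.** Section 7 names the amount of anaesthetic vaporised per minute of anaesthesia as the primary variable. The Power calculation in section 8 is built on that variable. From pilot experience it takes "a vaporizer consumption of 0.28 gr/min with a SD of 0.07", with the Flow-I machine "providing an estimated 0.03 gr/min reduction of vapor". It concludes that "a group size of 43 patients would be required in order to verify a significant difference" at p < 0.05 with 80% power. It then gives the total, "A total of 2 x 43 in all 86", and adds an allowance of 10–14 patients for losses to reach 100 recruited.

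The planned test is Student's t-test, or a Wilcoxon test if the data are not normal. Sections 1 and 5 randomise each patient to one machine or the other, so the two groups are independent.

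The sentence that opens section 8, directly before the power calculation, says: "As this is an explorative pilot study thus no formal sample size will be determined".

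**The concern.** A standardised difference of 0.03/0.07, about 0.43, is moderate. For two independent groups it needs clearly more than 43 patients in each for 80% power. The number 43 looks like the result of a formula for a single sample or for paired differences, which lacks the factor of 2 for comparing two independent means. It could equally be a correct per-group figure of 86 that was read as the total.

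The calculation is the only justification given for the number recruited, and it concerns the primary variable. If it is wrong, the trial is much more likely to miss the expected saving than the protocol tells its readers. A non-significant result reported alongside a claim of 80% power would also look more informative than it is.

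**Working it through.** **Inputs, all from the Power calculation in section 8**

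- Difference δ = 0.03 g/min.
- SD σ = 0.07 g/min, taken as common to both groups.
- α = 0.05. Sidedness is not stated, so two-sided is assumed and one-sided is also shown.
- Power 80%.
- Allocation 1:1, from 2 × 43 = 86.
- Standardised difference d = 0.03/0.07 = 0.4286. The mean of 0.28 g/min does not enter the formula.

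**Step 1: reproduce the plan's 43.** The one-sample or paired formula, by normal approximation, is

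n = (z₀.₉₇₅ + z₀.₈₀)² / d² = (1.960 + 0.842)² / 0.4286² = 42.7, rounded up to 43.

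This is the plan's figure, but the formula is not the one for this design.

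**Step 2: the formula for two independent means.**

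n per group = 2(z₀.₉₇₅ + z₀.₈₀)² / d² = 2 × 42.73 = 85.5, rounded up to 86.

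Solving with the noncentral t distribution gives 86.4, so 87 per group (power 79.8% at 86, 80.3% at 87). The total is 172 to 174 evaluable patients, against the plan's 86.

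**Step 3: one-sided alternative.** With z₀.₉₅ = 1.645 in place of 1.960, the normal approximation gives 67.3, so 68 per group. The t-test gives 68.01, so 69. Neither is near 43.

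**Step 4: power at the planned numbers.** With 43 per group the standard error of the difference is 0.07 × √(2/43) = 0.0151. The expected test statistic is then 0.03/0.0151 = 1.99, almost exactly the critical value, which is why power is close to one half.

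| Patients per group | Two-sided, t-test | Two-sided, normal | One-sided, t-test | One-sided, normal |
|---|---|---|---|---|
| 43 | 50.2% | 51.1% | 62.8% | 63.4% |
| 50 (no losses) | 56.4% | 57.3% | 68.6% | 69.1% |

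**Step 5: what would make the 80% claim true (t-test, two-sided).**

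| Patients per group | Difference detectable with 80% power, SD 0.07 | SD needed for 80% power, difference 0.03 |
|---|---|---|
| 43 | 0.043 g/min | 0.049 g/min |
| 50 | 0.040 g/min | 0.053 g/min |

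The normal approximation gives 0.042 and 0.050 at 43 per group, which is the same for practical purposes.

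**Step 6: precision.** At 43 per group, with SD 0.07, the half-width of the 95% confidence interval is about 1.99 × 0.0151 = 0.030 g/min. That equals the whole expected saving.

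**The case against.** Several points can fairly be made for the plan.

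- **Sidedness.** The plan does not say the test is two-sided, and its hypothesis is directional. One-sided power is higher, at 63% to 69%, but still well short of 80%.
- **Losses.** The 10–14 patients are an allowance, not a forecast. Section 6 has the vaporiser weighed before and after each anaesthetic, so the primary variable may lose few patients. Two-sided power is therefore better given as 50% to 56%.
- **Cause.** The plan shows no formula. That the factor of 2 was dropped is an inference. The match to 43 holds for the normal approximation, while the one-sample t-test solution is 44.7. Reading 86 per group as the total explains the numbers equally well. The discrepancy does not depend on which explanation is right.
- **Pilot status.** Section 8 opens by calling the study exploratory, and a pilot needs no power calculation. But the plan goes on to make an explicit 80% claim, based on an earlier pilot, and sets recruitment from it. Sections 1 and 3 also describe the aim as testing a hypothesis. A pilot could justify 100 patients on feasibility, but that would not make the power statement correct.
- **Interpretation.** The documents contain no rule for reading a non-significant result, so any misreading is a risk and not something the plan commits to.

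These points affect the wording and the range to quote. None of them brings power to 80%. The Wilcoxon alternative does not help either: under the normal model used for planning it has no more power than the t-test.

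**Conclusion.** The power statement is wrong as written. On the plan's own inputs, two independent groups need 86 to 87 evaluable patients each for 80% two-sided power, twice the stated number. The planned trial has 50% power at 43 per group and at most 56% if nobody is lost. One-sided, the range is 63% to 69%. This rests on a common SD of 0.07, a true difference of 0.03 g/min, equal allocation and α = 0.05. The contradiction between the opening sentence of section 8 and the calculation below it is a second, smaller defect in the same place.

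**What to change.** If enrolment stays at 100, replace the power statement with text such as: *With an SD of 0.07 g/min and a true difference of 0.03 g/min, 43 (50) evaluable patients per group give about 50% (56%) power at a two-sided 5% level. The difference detectable with 80% power is 0.043 (0.040) g/min.* State the sidedness of the test. Delete the sentence saying that no formal sample size will be determined, or reword it to agree with the calculation. This costs wording only, but the stated power becomes less favourable.

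If the sponsor wants to keep 80% power for 0.03 g/min, 172 to 174 evaluable patients are needed. Taking the loss allowance as 10% to 14%, that means recruiting between 172/0.90 = 191.1 (192 for equal groups) and 174/0.86 = 202.3 (204). Alternatively, a smaller SD or a larger difference would have to be justified from the pilot data. Either choice should be made explicitly.

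It would also be sensible, though the correction does not require it, to say that the primary result will be reported as an estimate with a 95% confidence interval and that a non-significant result will not be read as showing no difference.

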## 1. Protocol Summary

**Title of study:** Low fresh gas flow during elective general anaesthesia -  
A study comparing the Flow-I and a conventional anaesthetic machine with a circle system including a bellow reservoir.

**Institution:** Department of Anaesthesia & Intensive Care Danderyds University Hospital, Institution for Clinical Science, Karolinska Institutet, Stockholm, SWEDEN

**Study time-lines:** Patients inclusion in 8 month, study report in 12 month, from initiation of patient into study.

**Objective:** To test the hypothesis that the Flow I patient circle and fresh gas generation provides a faster and less gas consuming equilibrium and maintenance of general anaesthesia as compared to a conventional anaesthetic machine including a breathing circle with a below reservoir.

The study will compare Flow I to a conventional anaesthetic machine during routine elective general surgery in ASA 1-2 patients under general anaesthesia based on desflurane at a fresh gas flow of 1 L/min.

**Study design:** prospective, randomized study.

**Participants:** one hundred ASA 1-2 patients aged 20 – 60 years scheduled for elective general anaesthesia will be recruited. Patients will be randomized to Flow I or a conventional anaesthetic machine having general desflurane anaesthesia at a fresh gas flow of 1 l/min fresh gas flow.

**Duration of treatment:** Study protocol covers 72 hours after end of anaesthesia (follow-up of quality of recovery until day 3) .

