## **5. Randomisation**

Patients will be randomised on entering the operating theatre. The anaesthetist responsible for the patient will open an envelope in which the group will be noted. Each patient will have an inclusion number and each inclusion number will correspond to attribution to a treatment group in accordance with a randomization list pre-established by the envelope technique. The envelopes will be created from 2 random lists.

Patients will be randomised to

- Flow I
- Conventional anaesthetic machine

for maintenance of anaesthesia.

and subsequently to a fresh gas flow of

- 1 L/min FiO2 0.5 oxygen in air

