## 6. Anaesthesia Protocol

All patients will follow the routines of the department expect for the randomisation of anaesthetic machine

All patients will receive general anaesthesia in accordance to local practice expect for the randomisation of anaesthetic machine and maintenance of a fresh gas flow of 1 L/min during anaesthesia.

- Establishment of intravenous access, 1000 ml Ringeractetat.
- All patients will have preoxygenation FiO2 0.8 for 60 seconds including 3 “deep breath” prior to propofol (2.5 mg/kg) fentanyl (2 microgr/kg) co-induction will be administered until adequately anaesthetised.
- Intravenous continuous infusion remifentanil will be administered in a dose 3 µg/ml
- Muscle relaxation will be administer in accordance to local practice
- Patients will be ventilated with oxygen for 3 minutes and thereafter intubated.

No surgery will commence until a 1.5 MAC is reached.

The vaporizer will be weighed before and after each patient anaesthetised and gram inhaled anaesthesia per minute anaesthesia will be calculated

The fresh gas flow is increased to 4 L/min oxygen and 2 L/min air when last stitch is made.

- Time to extubation
- Time to state name and date of birth
- Time to discharge from the PACU

All patients will receive PONV prophylaxis in accordance to local routines.

- PONV during the first 24 hours after surgery
- Patients satisfaction

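### The primary g/min comparison has no effect measure fixed in advance and no centre term, although the Objective describes three centres

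*Combined protocol and SAP*

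**What the plan says.** Section 7 makes the primary variable the "amount of gas vaporized halogenated anaesthetic per minute anaesthesia". Section 6 says how it is obtained: "The vaporizer will be weighed before and after each patient anaesthetised and gram inhaled anaesthesia per minute anaesthesia will be calculated". The main measurements in the Protocol Summary name the same quantity.

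The only analysis text is the last sentence of Section 8: "Comparison of normally distributed variables will be done by Student's t-test, of variables not following a normal distribution by Wilcoxon Test". It covers all variables alike. It names no primary test, effect measure, confidence interval, criterion for normality or covariate.

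On centres, the Objective sets Flow-I against "the standard anaesthesia equipment/machine at the centre (multi-centre study; 3 centres"). The Protocol Summary gives one institution, "Department of Anaesthesia & Intensive Care Danderyds University Hospital". Section 5 says "The envelopes will be created from 2 random lists" and mentions neither centre nor stratification.

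**The concern.** The two branches of the rule answer different questions. A t-test concerns a difference in mean g/min, whereas a Wilcoxon rank-sum test does not estimate one. The Objective asks about vapour consumption and its cost, and the power calculation is framed as a reduction of 0.03 g/min. Only a mean difference converts directly into either. As written, the data decide whether the headline result is a mean saving or a rank comparison, and the plan does not say how that decision is made.

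If there are three centres with local machines and local routines, some of the spread in g/min may lie between centres. An analysis without centre leaves that spread in the error term. If allocation turns out to be stratified by centre, the unadjusted test is also conservative.

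**Working it through.** **Inputs.** From Section 8: control mean 0.28 g/min, SD 0.07, reduction 0.03, p < 0.05 (taken as two-sided), power 80%, 43 per group, 100 recruited. Assumed, because the documents do not give them: the share of variance between centres (0, 10 or 20%), the shape of the distribution, and a normality rule (Shapiro-Wilk at 5% in each arm).

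**The plan's own figure.** n per group = 2 × (1.960 + 0.842)² × 0.07² / 0.03² = 2 × 42.7 = 85.5, so 86 per group. The stated 43 appears only if the factor 2 is left out. Power at 43 per group: 0.03 / (0.07 × √(2/43)) = 1.987, and Φ(1.987 − 1.960) = 0.51 (0.50 by the noncentral t). The base power of about 0.50 used below comes from this separate error, not from the point made here.

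**Test choice, 43 per arm (simulated).**
- No true difference: choosing the test by the assumed Shapiro-Wilk rule rejects in 5.2% of trials with normal data and 4.8% with log-normal data. Taking the smaller of the two p-values, which the plan does not permit, gives about 6% (5.7-6.5% across runs).
- True difference 0.03: the two tests fall on opposite sides of 0.05 in 7.0% (normal), 9.8% (log-normal) and 10.6% (5% of cases shifted upwards) of trials. With no difference they do so in 2-3%.
- Power of t-test against Wilcoxon, same three shapes: 0.506 against 0.485, 0.501 against 0.524, 0.505 against 0.546. At 50 per arm: 0.564 against 0.543, 0.565 against 0.589, 0.569 against 0.622. With skew or outliers, the t-test therefore gives up 2-5 points.

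**Centre term.** If centres explain a share r of the variance, adjustment reduces the SD to 0.07 × √(1 − r). At 43 per arm:

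| r (assumed) | Formula, adjusted | Simulated, unadjusted | Simulated, adjusted |
|---|---|---|---|
| 0% | 0.51 | 0.50-0.52 | 0.48-0.51 |
| 10% | 0.55 | 0.49-0.51 | 0.52-0.55 |
| 20% | 0.60 | 0.50 | 0.58-0.60 |

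The simulations used three centres with total SD 0.07, split 1:1:1 or 3:2:1 in the main runs. The largest loss at r = 0 was 1.4 points. At 50 per arm and r = 20%, type I error went from 4.4% unadjusted to 4.6% adjusted under simple randomisation, and from 3.0% to 5.3% under stratified randomisation.

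**The minutes.** Section 7, Section 6 and the main measurements ("Amount anaesthesia agent consumed; Gram inhaled anaesthetic per minute anaesthesia") all divide by minutes of anaesthesia, and none says when these start or stop. Section 6 includes time in which agent may not be running, for example: "Patients will be ventilated with oxygen for 3 minutes and thereafter intubated". For scale, 60 delivery minutes at 0.28 g/min (assumed) is 16.8 g. Counting 10 further agent-free minutes gives 16.8/70 = 0.24 g/min. If the extra minutes are the same in both arms, this rescales the variable or adds noise. It biases the comparison only if they differ by arm or centre.

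**The case against.** **The test rule is conventional and does little harm.** It applies one test per variable and holds its type I error. The 7-11% discordance is not an error rate. Means may still be reported after a Wilcoxon test, and the power calculation already shows that a mean difference is of interest. Section 8 also calls the study an exploratory pilot, although it then gives a power calculation. Most of this stands, and it keeps the point minor. It does not settle in advance which result is primary.

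**The centre gain is conditional.** Only the Objective mentions three centres; the Protocol Summary names one institution, and other sections speak of the department. The 10% and 20% shares are assumptions. If the pilot SD came from one centre, adjustment would not bring the required group size below 86. Leaving centre out does not inflate type I error. All of this stands, so the first step is to reconcile the two sections. In addition, where each centre has its own comparator, the machine effect may differ by centre, and an additive model does not test that.

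**The stronger reading of the minutes.** A reader might infer that the minutes are mismatched to the weighed agent and that the primary result is biased. Suppose the minutes ran to extubation, with 60-90 minutes of vapour on, 10 minutes off, equal grams and emergence 3 minutes faster in one arm. That arm's g/min would then rise by 0.28 × T/(T + 7) − 0.28 × T/(T + 10) = 0.0107 (T = 60) to 0.0078 (T = 90), or 26-36% of the 0.03 target. None of those conditions is in the documents. They give no interval, so a mismatch cannot be shown, and the wash-out flow in Section 6 is the same in both arms.

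**Conclusion.** The point holds as a minor, cheap improvement. The plan does not fix the primary effect measure, and it omits centre while its Objective describes three centres with local comparators.

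A reader might infer that a data-dependent choice of test inflates the false-positive rate. The documents do not support that: the rule as written stays near 5%, and even picking the smaller p-value gives only about 6%. The loss is one of clarity and, if centres differ, of precision: about 2-5 points of power at an assumed 10% share and 8-10 points at 20%, against at most about 1.5 points lost if they do not differ. These gains require the Objective, not the Protocol Summary, to be right about the number of centres.

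The undefined minutes are missing detail, not an error in themselves.

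**What to change.** 1. Reconcile the Protocol Summary and the Objective on the number of centres.
2. In Section 8, for the primary variable, replace the test choice with: *The primary analysis is the difference in mean g/min between arms from a linear model with arm and centre, reported with a 95% CI; a Wilcoxon rank-sum test is a sensitivity analysis only.* Omit the centre term if the trial is run at one institution.
3. As a secondary clarification in Section 7, define one interval for the minutes, used identically in both arms and at all centres. Vaporiser on to the cessation of administration, from which secondary variable 2 is already timed, would serve. Vaporiser-off is chosen after randomisation by an anaesthetist who knows the arm, so total grams per case should be reported as well. For example, if one arm shuts off 5 minutes earlier in a 60-minute case (assumed), on-to-off still gives 0.28 g/min, while the saving over the whole case is 0.28 − 0.28 × 55/60 = 0.023 g/min.

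Cost: a few sentences, and perhaps only one new time on the CRF, vaporiser on. The statistical price is the small loss if centres do not differ, and about 2-5 points of power against Wilcoxon if the data are skewed or contain outliers, a case in which the sensitivity analysis gives a check. The model leaves untested whether the machine effect varies by centre.

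### The primary g/min comparison is planned without covariates; pre-specifying age, known before randomisation, would be a valid and modest gain in precision

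*Combined protocol and SAP*

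**What the plan says.** - **Outcome.** Section 7 (Outcome Variables) makes the primary variable the "amount of gas vaporized halogenated anaesthetic per minute anaesthesia". Section 6 (Anaesthesia Protocol) says how it is obtained: "The vaporizer will be weighed before and after each patient anaesthetised and gram inhaled anaesthesia per minute anaesthesia will be calculated". It is therefore an average over the whole anaesthetic.
- **Analysis.** The only analysis text is in section 8, under Power calculation: "Comparison of normally distributed variables will be done by Student's t-test", with a Wilcoxon test for other variables. No covariate, regression model or stratification factor is named anywhere.
- **Age.** The inclusion criteria in section 3 read "Age 20 to 60 years". Section 5 randomises patients as they enter the theatre, so age is already known and the machine cannot affect it.
- **Where age enters.** The first secondary variable in section 7 is the time from 1 to 1.5 "age adjusted MAC with a constant 1 L/min. and a dialled 3 MAC". Section 6 holds surgery until 1.5 MAC is reached. Afterwards the setting follows clinical need.
- **Planning values.** Section 8 assumes "a vaporizer consumption of 0.28 gr/min with a SD of 0.07" and a machine "providing an estimated 0.03 gr/min reduction of vapor".

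**The concern.** The plan treats anaesthetic requirement as dependent on age when it defines the wash-in target, but leaves age out of the comparison of how much agent is used. With a common vaporiser setting during wash-in, an older patient has a lower absolute concentration to reach and may leave that high-delivery phase sooner. If depth during surgery also follows an age-related requirement, part of the patient-to-patient variation in g/min is predictable from a value already on the case record form. An unadjusted test leaves that part in its error term.

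What is at stake is precision. At 43 per group the planned comparison has a 95% confidence interval about as wide on each side as the 0.03 g/min it seeks, so a baseline predictor that costs almost nothing to use deserves consideration. Naming it in advance also removes any later choice between adjusted and unadjusted results.

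**Working it through.** **Inputs from the documents (section 8):** mean 0.28 g/min, SD 0.07, difference 0.03, p < 0.05 (sidedness not stated, taken as two-sided), 80% power, 43 per group. Age range 20 to 60 (section 3).

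**Inputs assumed:** the slope of g/min on age and the spread of ages. The documents give neither. They also do not say whether the pilot SD of 0.07 is raw or age-adjusted; I take it as raw.

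**1. The plan's own figure.** For two independent groups, n per group = 2 × (SD × (1.960 + 0.842) / difference)² = 2 × (0.07 × 2.802 / 0.03)² = 85.5, so 86 per group. The stated 43 is not reproduced. It appears only when the factor 2 is left out (42.7).

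**2. Power of the planned test.** SE = 0.07 × √(2/43) = 0.0151. A noncentral t calculation gives 50.2% power at 43 per group and 56.4% at 50 per group. The 95% CI half-width at 43 per group is 1.989 × 0.0151 = 0.0300 g/min.

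**3. Central slope.** If requirement falls 6% per decade and consumption is strictly proportional to it, the slope is 0.28 × 0.06 / 10 = 0.0017 g/min per year, downward. I also use 0.001 and 0.0025, which correspond to 3.6% and 8.9% per decade, and zero.

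**4. Variance explained.** Uniform ages over 20 to 60 have SD 40/√12 = 11.55 years. R² = (slope × age SD / 0.07)². For the central slope, (0.0017 × 11.55 / 0.07)² = 0.079.

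**5. Adjusted power at 43 per group.** Residual SD = 0.07 × √(1 − R²). Two costs are charged: one degree of freedom (84 to 83), and an expected variance inflation for chance age imbalance of 1 + 1/(2n − 4) = 1 + 1/82, which multiplies the SE by 1.006.

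| Slope (g/min per year, downward) | R² | Residual SD | SE with inflation | Power |
|---|---|---|---|---|
| unadjusted | – | 0.0700 | 0.0151 | 50.2% |
| 0 | 0 | 0.0700 | 0.0152 | 49.7% |
| 0.001 | 0.027 | 0.0690 | 0.0150 | 50.8% |
| 0.0017 | 0.079 | 0.0672 | 0.0146 | 53.0% |
| 0.0025 | 0.170 | 0.0638 | 0.0138 | 57.3% |

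At the central slope the CI half-width goes from 0.0300 to 1.989 × 0.0146 = 0.0290 g/min. Before the two costs, the gain equals 1/(1 − 0.079) − 1 = 9% more patients (3% and 20% at the outer slopes).

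**6. Narrower age spread.** With an age SD of 8 years, R² shrinks by (8/11.55)² = 0.48, to 0.013, 0.038 and 0.082. Power becomes 50.2%, 51.2% and 53.1%.

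**7. Break-even.** Adjustment helps once the within-arm correlation of age with g/min exceeds about 0.11.

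**8. What would restore 80%.** By the normal approximation, R² would have to be 1 − 43/85.5 = 0.50 at 43 per group, or 1 − 50/85.5 = 0.42 at 50 per group.

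**The case against.** The strongest reply is that nothing here is wrong. Under randomisation the unadjusted t-test controls its type I error, and its standard error already allows for chance differences in age between arms. That stands in full: a reader might infer that the planned result would be biased by age, and the documents do not support that.

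Second, a reader might infer from the age-adjusted target that age governs delivery throughout. The documents tie age only to the wash-in step. There the vaporiser setting is the same for everyone, so age can change the length of the step but not the setting. After that, delivery follows clinical need with no age-based target, and the outcome averages over both phases. The link from age to g/min is plausible but indirect, and its size is an assumption. This stands, and it is why a zero slope belongs in the table.

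Third, adjustment is not free. It uses a degree of freedom, slightly lowers power if age does not matter, and has to be reconciled with the planned Wilcoxon route. This stands too, but the loss is about half a percentage point.

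Fourth, section 8 calls the study an exploratory pilot. The same section nevertheless gives a power calculation for this outcome, so precision on it is a fair subject.

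**Conclusion.** The point holds as an optional but worthwhile efficiency improvement. Age is complete, fixed before randomisation and plausibly related to the primary outcome, and the plan does not use it. Under the proportionality assumption, with ages uniform over 20 to 60, adjusting moves power at 43 per group from 50% to about 53%, with 51% to 57% across the slopes tried. The gain is smaller if ages are less spread out, and there is a loss of about 0.5 points if age is not prognostic.

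It would be tempting to read age adjustment as a remedy for the shortfall in power. It is not: that would need age to explain 40% to 50% of the variance, against about 8% in the central case. The group size in section 8 is a separate problem and has to be settled on its own terms.

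**What to change.** In section 8, state that the primary analysis is a linear model of g/min on machine with age in years as a pre-specified linear covariate, reporting the adjusted mean difference and its 95% CI. Keep the planned unadjusted t-test or Wilcoxon test as sensitivity analyses, with the Wilcoxon test covering clear non-normality. Fix this before any outcome data are examined by arm.

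The cost is a short addition to the text, one degree of freedom, and a negligible loss of power if age turns out not to matter. No new data or patients are needed. Since the Objective section describes three centres, each comparing Flow-I with its own standard machine, the authors could decide at the same time whether centre belongs in the model; that is a separate question.
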